Description of location(s) where consent will be obtained:

George E Wahlen Department of Veterans Affairs Hospital, Salt Lake City Health Care System.

Description of the consent process(es), including the timing of consent:

Consent process is now part of the IRB study # 00082763. No separate consent process will be used.

Requested Waivers/Alterations of Consent:

Waiver of Informed Consent VA Waiver of Consent for Recruitment Purposes Only

Procedures:

-Patient selection

All patients selected to participate in the "Safety Study of Percutaneous Osseointegrated Implants for Prosthetic Attachment (IRB #00082763)" will participate in this study. As this is safety evaluation study, subjects will not be randomized. Follow-up end point will be 1 year post 2nd stage surgery.

Patients will be consented through IRB study # 00082763.

- Obtaining consent

Patients are consented as part of the IRB #00082763 consenting process

- Sample collection

Samples (skin swabs, tissue and blood) for this study will come from the samples collected and tissue-banked as part of the IRB # 00082763.

Collection process is described in IRB # 00082763. Briefly, samples will be collected from each patients at different pre- and post-operative time points (see below).

Pre-op stage 1/day of the procedure, 3+/-7 days of stage 1 post-op, pre-op of stage 2/day of procedure, day 7 +/- 7 days of stage 2, 2 wk +/- 14 days of Stage 2, and 6wk +/- 14 days, 3, 6,9, 12 mo +/- 30 Days of stage 2.

-Analysis

-Reporting

Procedures performed for research purposes only:

Statistical Methods, Data Analysis and Interpretation

Statistical analysis: A sample size of n=10 patients is planned to be used.

Sample Size Justification. A sample size of n=10 patients will be used. Even if the specific comparisons, which involve a single predictor variable, described for Aims 1 to 3 reveal trends that are not statistically significant, it would be sufficient to show that overall model fit is significant. That is, a significant multivariable curvilinear correlation with pro-inflammatory cytokines, for example, would demonstrate that Bio-Plex array is potentially a sensitive indicator of inflammation and/or infection, provided that a visible shift in the graphed growth curve occurs

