with the onset of inflammation and/or infection. With a sample size of 10, there is 80% power using a two-sided alpha 0.05 comparison, to detect a correlation of $r=0.71$ or greater. Converting this to a coefficient of determination, $r^2 = 0.50$, the multivariable model would have to account for 50% of the variability in pro-inflammatory cytokines concentration. Since cytokines is measurable, going up or down across healing time in an anticipated fashion, with time being one of the predictor variables making up the multivariable curvilinear correlation, it is reasonable to assume that this magnitude of correlation will be observed in this study. Furthermore, the repeated measurements increase the statistical power somewhat. The study, then, is adequately powered to demonstrate the feasibility of microbiota, and pro-inflammatory cytokines/markers as indicators of inflammation and/or infection.

Microbiota analysis

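### The 80% power at n=10 belongs to a one-predictor test but is applied to the overall fit of a multivariable model, where power on the same basis is at most about 61%

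*Combined protocol and SAP*

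**What the plan says.** All of this is in the combined protocol and SAP, under Statistical Methods, Data Analysis and Interpretation, in the Sample Size Justification, except where noted.

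- Two kinds of test are distinguished. The first is "the specific comparisons, which involve a single predictor variable", which the plan accepts may not reach significance. The second is the fallback: "it would be sufficient to show that overall model fit is significant". The plan also asks for a visible shift in the plotted curve when inflammation or infection begins.
- The power statement is: "With a sample size of 10, there is 80% power using a two-sided alpha 0.05 comparison, to detect a correlation of $r=0.71$ or greater".
- The correlation is then squared to 0.50, with the consequence that "the multivariable model would have to account for 50% of the variability in pro-inflammatory cytokines concentration".
- The model has several predictors, "with time being one of the predictor variables making up the multivariable curvilinear correlation". The number of terms is not given.
- Repeated measurement is mentioned only after the 80%: "the repeated measurements increase the statistical power somewhat". Under Procedures, Sample collection, "samples will be collected from each patients at different pre- and post-operative time points"; ten are listed.
- The conclusion is: "The study, then, is adequately powered to demonstrate the feasibility of microbiota", together with the inflammatory markers.

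**The concern.** The power of an overall F test depends on how many terms the model has. Each added term takes one degree of freedom from the residual and adds one to the numerator. A correlation between two variables is the one-term case, so the R² detectable with 80% power there is not the R² detectable with 80% power in a model of two or more terms. The plan makes this transfer with no adjustment, and it does so for the test it treats as sufficient for success.

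No other calculation supports n=10 or the claim of adequate power. If the claim stands, a non-significant overall fit could be read as evidence against a model explaining half the variability, from a study thought to have 80% power to find one. The plan also foresees expansion to 200 patients if this pilot succeeds, so the sensitivity attached to its success criterion should be right.

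**Working it through.** **Inputs from the plan:** n = 10; two-sided alpha 0.05; r = 0.71; R² = 0.50 for the model; at least two model terms, since time is one of several predictors. **Not in the plan:** the exact number of terms p. The range 2 to 4 is shown.

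**Step 1. Reproduce the stated 80%.** For one fixed predictor and 10 independent rows:

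- r² = 0.71² = 0.5041
- noncentrality λ = n·r²/(1 − r²) = 10 × 0.5041/0.4959 = 10.17
- F with 1 and 8 df, 5% critical value 5.32
- power = 79.7%, which matches the plan

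Other readings at r = 0.71 do not match: two-sided Fisher z 65%; both variables random (bivariate normal) 70%; one-sided Fisher z 76%; one-sided noncentral t 90%. The plan's figure is therefore a one-predictor result with one observation per patient.

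**Step 2. Apply the same basis to the overall fit.** With R² = 0.50, λ = 10 × 0.50/0.50 = 10, and the test is F with p and 10 − p − 1 df:

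| Terms p | df | 5% critical F | Power at R² = 0.50 | R² needed for 80% power |
|---|---|---|---|---|
| 1 | 1, 8 | 5.32 | 79.1% | 0.51 |
| 2 | 2, 7 | 4.74 | 61.4% | 0.60 |
| 3 | 3, 6 | 4.76 | 46.7% | 0.68 |
| 4 | 4, 5 | 5.19 | 34.7% | 0.75 |

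Simulation with 100,000 draws per row gives 79.3%, 61.3%, 46.6% and 34.6%. Using the unrounded 0.5041 in place of 0.50 gives 62.1% for two terms.

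**Step 3. Rows needed.** With two terms at R² = 0.50, 13 rows give 79.3% and 14 rows give 83.5%, so 14 are needed for 80% power.

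**Step 4. How much repeated measures could change this.** The plan gives no inputs here, so every one is an assumption: patient effects removed, independent residuals, fixed predictors, k usable visits for each of 10 patients, and a within-patient R² written R²w. Then the df are p and 10(k − 1) − p, and λ = 10(k − 1)·R²w/(1 − R²w). For example, k = 3 and R²w = 0.50 give λ = 20 × 1 = 20.

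| Usable visits k | R²w | Power, p = 4 to p = 2 |
|---|---|---|
| 2 | 0.50 | 39% to 64% |
| 3 | 0.50 | 89% to 97% (rounded up from 96.5%) |
| 5 | 0.50 | 99.9% or more |
| 3 | 0.10 | 15% to 22% (rounded up from 21.5%) |
| 10 | 0.10 | 69% to 80% |

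Correlated residuals would change these values. The table shows only that the answer runs from very low to near certain, depending on quantities the plan leaves unstated.

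**The case against.** The strongest reply is that the 61% describes an analysis nobody intends to run. The plan has ten collection points per patient, makes time a predictor, and says that repeated measurement adds power. The 80% can then be read as a base figure before the longitudinal gain. At the plan's own R² of 0.50, the illustration above gives 89% or more with only three usable visits. The reference list consists of two papers on correlation with repeated observations, which suggests such an analysis was in mind. Nothing is miscalculated in the narrow sense, since 79.7% rounds to 80% and 0.71² is 0.504. The sample size is fixed by the parent study, and this is a feasibility pilot.

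Much of this stands. The 61% must not be quoted as the power of the study, and the claim of adequate power has not been shown to be false. But the plan attaches 80% to a sample size of 10, carries it to the multivariable model, and only then mentions repeated measurement, with no model, number of visits, within-patient correlation or figure. The two references are not cited in the text and supply no calculation. The plan's argument that a correlation of this size is likely to be observed concerns whether the effect exists, not the power to detect it. A pilot need not claim power, but this one does.

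**Conclusion.** The concern holds. The stated 80% is correct for one predictor and one observation per patient, and wrong for the overall multivariable fit to which the plan applies it. On the same basis the power for that criterion is at most 61% (62% with r² unrounded), and lower with each further term.

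This rests on reading the multivariable model as having at least two terms, which the plan's wording supports, and on fixed predictors, the basis that reproduces the plan's own figure. Whether the planned repeated-measures analysis is adequately powered is undetermined. The error affects a stated claim, not enrolment, and should be corrected.

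**What to change.** 1. Label the figure for what it is. Suggested wording: With 10 patients and one observation per patient, a two-sided test at alpha 0.05 has 80% power for a correlation of 0.71 or more with a single predictor, the predictor being treated as fixed. Optionally add that power is about 70% if both variables are treated as random.
2. Remove the statement that carries this to R² = 0.50 for the multivariable model.
3. State the number of model terms and the unit of analysis. Then give either the matching detectable R² (about 0.60 for two terms with one row for each of 10 patients) or a power for the planned repeated-measures model, with its usable visits and within-patient assumptions. The second is preferable if that is the analysis intended, because the first describes one row per patient only.
4. Delete or qualify the claim of adequate power unless the calculation in step 3 supports it.

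The cost is wording and one small calculation. The repeated-measures option also requires the sponsor to state assumptions that the plan does not now contain. The resulting figure may be less favourable than 80%. No patients, samples or visits are added.

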The critical limiting factor to the prior U.S. introduction of this technology has been an up to 30% infection rate at the implant/skin interface in European patients. Evolving designs and surgical techniques have lowered this incidence, but it remains remarkable that 70% to perhaps 95% of European patients now remain infection free by simply using mild soap and shower hygiene at the stoma, and avoiding the use of antibiotics. In fact antibiotics and disinfectants have been found to be counter productive and lead to antibiotic resistance. It is increasingly evident that the key to this improbable success is the biology and presence of a mutualistic-commensal microbiota at the skin/implant interface. These “good bacteria” are the “guard dogs at the gate”.

Microbiome studies: Traditionally, wound microbiotas have been characterized by culture based assays. Cultures, however, account for only 3% of the bacterial strains actually present. A recent study, reported that, on average, culturing techniques underestimated microbial load by 2.34 logs ($P < 0.0001$), and in some cases greater than 6 logs. Bacterial cultures, because they are designed to select for specific pathogens, are unable to grow and recognize most of the other resident skin microbiota. These non-molecular techniques do not allow a full understanding of the complexity of stomal colonization in both the diseased and healthy states.

The relationships between the bacterial subsets within an ecological community are complex. There is strong evidence to suggest that microbes that are commonly thought of as pathogens can live commensally on the skin. In fact, bacteria from the genera *Staphylococcus*, *Corynebacterium*, *Propionibacterium*, *Streptococcus* and *Pseudomonas*, may directly benefit the host (mutualism) and only rarely will they become pathogens. Recent developments in molecular based technology have now paved the way to more advanced genome based techniques for identifying bacterial ecologies (microbiome). Techniques based upon distinct bacterial molecular markers, such as 16S rRNA are now being employed to truly understand the complexity and complicity of the human microbiome.

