The purpose of this study is to investigate the clinical implementation of a new percutaneous prosthetic attachment system (Safety Study of Percutaneous Osseointegrated Implants for Prosthetic Attachment; separate IRB # 00082763) by determining the resident microbial ecology of the implant exit site and to simultaneously study the systemic and local stomal immune responses. We will use two, state-of-the-art, pre- and post-surgery bacterial monitoring technologies: these procedures are intended to facilitate the early prediction, detection, and treatment of infection, as well as to provide follow-up data that can potentially be used to advantageously manipulate the stomal microbial environment in future clinical trials.

Objectives

The objective of this study is to follow 10 patients implanted with a percutaneous osseointegrated exoprosthetic docking system (PODS) for a period of one year. This PODS

technology requires invasive surgery to skeletally attach a metal implant, which protrudes from the long bone and exits the stump skin of the amputee patient (IRB# 00082763, as above). All stomas are colonized by local skin bacteria; colonization does not necessarily result in infection. Over time, the presence of this skin penetrating foreign object (implant) will cause measurable changes in the bacterial population (microbiota) at and around the PODS exit site.

It is anticipated that the evolving microbiota, in concert with measurable changes in the local and systemic cytokine responses, will reveal patterns associated with mutualistic-commensal bacteria and/or pathogenic bacteria related to the stages of chronic wound healing. These patterns could be used to determine the presence of a stable uninfected stoma or the progression of a stomal infection. Hopefully, this information will allow timely intervention to prevent infection, i.e. by detecting early stages of infection or discerning common patterns of stable mutualistic-commensal bacterial strains, effective intervention protocols (antibiotics, probiotics or manipulation of the stomal and skin microbiota) may be developed to avoid patient morbidity and assure implant survival.

The study aims will test the following:

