4. Has, in the opinion of the investigator, normal cognitive function and no physical limitations, addictive diseases, or underlying medical conditions including tobacco use (continued testing for tobacco use will be performed at screening) that may prevent the subject from being an appropriate study candidate.
5. Is willing, able, and committed to participation in baseline and follow-up evaluations for the entire duration of the study.
6. Can provide written informed consent to participate.

Exclusion Criteria:

A potential subject will be excluded from study participation if he/she meets any of the following criteria (the IRB 00082763 study criteria)

1. Is currently on active or reserve military duty
2. Has experienced systemic bacterial infection or localized infection at the stump site within the previous 6 months
3. Has had more than 1 limb amputated
4. Has a body mass index (BMI) ≥ 30
5. Has insulin dependent diabetes mellitus (IDDM) or has adult onset DM with a glycated hemoglobin (HbA_{1c}) > 53 mmol/mol (7.0%) at screening

6. Has residual femur bone length of less than 25% of the length of the contralateral femur.
7. Has clinically diagnosed vascular compromise proximal to the surgical site
8. Is pregnant at the time of surgery or plans to become pregnant within the first year of follow-up
9. Has evidence of recent tobacco use (urine cotinine test > 300 ng/mL [1703 nmol/L]) and is not committed to a smoking-cessation program
10. Has renal insufficiency (defined as serum creatinine of \geq 1.8 mg/dL) or is currently receiving renal dialysis
11. Is currently involved in or plans to be involved in high levels of physical activity (competitive sports, heavy physical labor, etc) during the first 12 months of the rehabilitation stage
12. Has muscular, neurologic or vascular deficiencies that may compromise the bone or soft tissue healing of the affected extremity
13. Has anemia characterized by a hemoglobin of \leq 11 g/dL at the time of surgery
14. Is currently on oral anticoagulation (excluding low-dose aspirin for cardiac prophylaxis)

Design

Other

Retrospective sample analyses

Study Procedures

Recruitment/Participant Identification Process:

Only patients, who will be recruited and consented to participate in IRB#00082763 study, will participate in this "Microbiome" study to retrospectively assess the progression of wound and stomal healing and/or the occurrence of infection, as a safety survey and previously described.

Informed Consent:

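### The adequacy claim covers infection, but the calculation behind it concerns healing time only, and the plan's own infection proportions imply 0.5 to 3 infected patients among ten

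*Combined protocol and SAP*

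**What the plan says.** The Sample Size Justification (Statistical Methods, Data Analysis and Interpretation) fixes the sample at ten patients. It states: "With a sample size of 10, there is 80% power using a two-sided alpha 0.05 comparison", "to detect a correlation of $r=0.71$ or greater". It converts this to a coefficient of determination of 0.50, so that "the multivariable model would have to account for 50% of the variability in pro-inflammatory cytokines concentration". It considers a correlation of that size plausible because cytokines move in an expected direction as healing proceeds, and time is one of the predictors.

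A proviso precedes the calculation. A significant overall fit would mark the cytokine array as a potentially sensitive indicator, as long as the plotted curve visibly shifts when inflammation and/or infection begins. The section then concludes that the study is "adequately powered to demonstrate the feasibility of microbiota, and pro-inflammatory cytokines/markers as indicators of inflammation and/or infection".

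Infection figures appear only in the Background and Introduction: "an up to 30% infection rate at the implant/skin interface in European patients", and, with newer designs and techniques, "70% to perhaps 95% of European patients now remain infection free". Purpose and Objectives says of the microbiota and cytokine patterns: "These patterns could be used to determine the presence of a stable uninfected stoma or the progression of a stomal infection".

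**The concern.** The closing sentence makes one adequacy statement about two different things. Inflammation after surgery happens in every patient, so ten patients can inform a description of it. Infection happens in only some patients, and a marker cannot be shown to indicate infection, even as a matter of feasibility, unless some patients become infected. The justification never asks how many that will be.

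The *and/or* hides the gap. A significant model fit and a visible shift after two operations would satisfy both the proviso and the conclusion with no infected patient. A result that reflects healing alone could then be reported as evidence that the markers indicate infection.

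**Working it through.** **1. The plan's own figure.** Inputs from the Sample Size Justification: n = 10, two-sided alpha 0.05, r = 0.71. For one fixed predictor, the test of the slope has 8 degrees of freedom and noncentrality √n × r / √(1 − r²) = 3.162 × 0.71 / 0.704 = 3.19. The power is 79.7%, which matches the stated 80%. The match depends on the method: the Fisher z approximation gives 65.1%, and simulation with both variables random and normal gives 69.9%. I accept the 80% here, because the present point does not turn on it.

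**2. What that figure is about.** Its inputs are a patient count, an error rate and a correlation. The correlation is defended by cytokine change over healing time. No infection proportion, count or definition is used. The 80% could be fully achieved in ten patients who never become infected, so it carries no information about infection.

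**3. Expected infections.** The Background's 70% to 95% infection free means 30% to 5% infected. Neither the period nor the definition of infection is given. I assume that the proportions apply to the one-year follow-up and that patients are independent. The 15% row is an intermediate value for illustration. With proportion p:

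- expected number infected = 10p
- P(none) = (1 − p)^10
- P(at most one) = (1 − p)^10 + 10p(1 − p)^9

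| p | Expected infected | P(none) | P(at most one) |
|---|---|---|---|
| 5% | 0.5 | 0.599 | 0.599 + 0.315 = 0.914 |
| 15% | 1.5 | 0.197 | 0.197 + 0.347 = 0.544 |
| 30% | 3.0 | 0.028 | 0.028 + 0.121 = 0.149 |

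**4. Does the proviso close the gap?** Suppose that nobody is infected. Every patient still has two operations, and cytokines rise and fall around them. The model fit may be significant and the curve may visibly shift at the onset of inflammation. Because the proviso accepts inflammation *or* infection, it is met, and the closing sentence then covers both.

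**5. Does anything else in the plan close it?** The Microbiota analysis compares samples before and after surgery. The whole-blood expression analysis compares later time points with the two pre-surgery samples. The rank-sum test is said to compare populations, but these are not defined by infection status. This document has no comparison by infection status and no rule for the case of no infections.

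**The case against.** The strongest reply is that the plan is more cautious than the concern allows. It speaks of feasibility and of a potentially sensitive indicator, and it attaches a proviso. Its two aims are to characterise the microbiota and to compare and correlate biomarkers over wound healing. Separating stable from infected stomas is offered as a possible use, and the benefit of predicting infection is placed in future trials. This is fair: a reader might infer that telling infected from uninfected stomas is the study's stated objective, and the text does not go that far. The closing sentence nevertheless says adequately powered and names infection. Feasibility as an infection indicator still needs infections, and the proviso does not require one.

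Other stronger readings also go beyond the documents:

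- A reader might compute the smallest attainable p-value for infected against uninfected patients (0.20 with one against nine), or exact limits for sensitivity. The plan specifies neither a comparison of that kind nor a sensitivity endpoint, so these figures would judge an analysis that is not planned.
- A reader might infer from the eligibility criteria (for example "Has experienced systemic bacterial infection or localized infection at the stump site within the previous 6 months") that these patients are at low risk, so that the 5% end applies. The plan does not say so, and nothing shows that the European patients were less selected.
- A reader might infer that an unsupported infection claim would drive the anticipated 200-patient expansion. The plan ties expansion to the success of the pilot trial, not to a marker claim.

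Two further points stand in part. At 30%, at least one infection is likely (97%), as are at least two (85%), so a lack of infections is not certain. Within-patient courses and repeated samples also add information, and the parent study (IRB 00082763, not supplied) may define infection or allow extra sampling. Neither point supplies the missing basis for the adequacy claim. Repeated samples do not add infected patients, and even three expected infections were never considered in the justification.

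**Conclusion.** The concern holds for the infection half of the closing sentence. That half has no supporting calculation. On the plan's only infection figures, ten patients give 0.5 to 3 expected infections, with a chance of none from 60% down to 3% and of at most one from 91% down to 15%. These numbers rest on applying European proportions, with no stated period or definition, to one year of follow-up in independent patients. The absence of support does not rest on them, because it follows from what the power calculation contains.

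The inflammation and healing half is not challenged here. In an exploratory ten-patient study whose enrolment is tied to a parent trial, this is a correction of a stated claim and not a fault that invalidates the design. It should be made, but it ranks below the most serious class of finding.

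**What to change.** Amend the Sample Size Justification as follows:

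1. Limit the adequacy statement to the inflammation and healing response over time.
2. Split inflammation and infection into two conclusions, both in the closing sentence and in the proviso about a visible curve shift.
3. State that infection findings are descriptive only, that 0.5 to 3 infected patients are expected under the Background's proportions, and that the observed number will be reported. The analysis sections are written in the past tense, so that number may already be known.
4. State that a shift explained by surgery or healing does not support an infection-indicator conclusion, and that no such conclusion is drawn if no infection occurs.

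I would not add a minimum number of infections for evaluability. Once infection is descriptive, a threshold has no inferential basis, and it would set aside a single well-documented course that is worth reporting.

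The cost is wording only, with no extra patients, samples or assays. The downside for the sponsor is a less favourable stated claim.
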